13 REPORTING, PUBLICATIONS AND NOTIFICATION OF RESULTS

13.1 AUTHORSHIP POLICY

Ownership of the data arising from this study resides with the study team. Authorship in any ensuing publications will be conducted as per the International Committee of Medical Journal Editors standards.

15 APPENDIX

Headaches.....	0	1	2	3	4
Feelings of Dizziness	0	1	2	3	4
Nausea and/or Vomiting	0	1	2	3	4
Noise Sensitivity,					
easily upset by loud noise	0	1	2	3	4
Sleep Disturbance.....	0	1	2	3	4
Fatigue, tiring more easily	0	1	2	3	4
Being Irritable, easily angered	0	1	2	3	4
Feeling Depressed or Tearful.....	0	1	2	3	4
Feeling Frustrated or Impatient	0	1	2	3	4
Forgetfulness, poor memory	0	1	2	3	4
Poor Concentration	0	1	2	3	4
Taking Longer to Think	0	1	2	3	4
Blurred Vision	0	1	2	3	4
Light Sensitivity,					
Easily upset by bright light.....	0	1	2	3	4
Double Vision	0	1	2	3	4
Restlessness	0	1	2	3	4

Appendix I: Rivermead Post-concussion Questionnaire

PATIENT HEALTH QUESTIONNAIRE - 9				
Over the last 2 weeks, how often have you been bothered by any of the following problems?	Not at all	Several days	More than half the days	Nearly every day
1. Little interest or pleasure in doing things	0	1	2	3
2. Feeling down, depressed, or hopeless	0	1	2	3
3. Trouble falling or staying asleep, or sleeping too much	0	1	2	3
4. Feeling tired or having little energy	0	1	2	3
5. Poor appetite or overeating	0	1	2	3
6. Feeling bad about yourself — or that you are a failure or have let yourself or your family down	0	1	2	3
7. Trouble concentrating on things, such as reading the newspaper or watching television	0	1	2	3
8. Moving or speaking so slowly that other people could have noticed? Or the opposite — being so fidgety or restless that you have been moving around a lot more than usual	0	1	2	3
9. Thoughts that you would be better off dead or of hurting yourself in some way	0	1	2	3
FOR OFFICE CODING ____ + ____ + ____ + ____ =Total Score: _____				

If you checked off any problems, how difficult have these problems made it for you to do your work, take care of things at home, or get along with other people?

Not difficult at all 	Somewhat difficult 	Very difficult 	Extremely difficult 
---	---	---	--

Appendix II: PHQ-9 Questionnaire

PITTSBURGH SLEEP QUALITY INDEX (PSQI)

1. During the past month, when have you usually gone to bed at night?
2. During the past month, how long (in minutes) has it usually taken you to fall asleep each night?
3. During the past month, when have you usually gotten up in the morning?
4. During the past month, how many hours of actual sleep did you get at night? (This maybe different than the number of hours you spend in bed.)

5. During the past month, how often have you had trouble sleeping because you...

(a) Cannot get to sleep within 30 minutes.	Not during the past month	Less than once a week	Once or twice a week	Three or more times a week
(b) Wake up in the middle of the night or early morning.	Not during the past month	Less than once a week	Once or twice a week	Three or more times a week
(c) Have to get up to use the bathroom.	Not during the past month	Less than once a week	Once or twice a week	Three or more times a week
(d) Cannot breathe comfortably.	Not during the past month	Less than once a week	Once or twice a week	Three or more times a week
(e) Cough or snore loudly.	Not during the past month	Less than once a week	Once or twice a week	Three or more times a week
(f) Feel too cold.	Not during the past month	Less than once a week	Once or twice a week	Three or more times a week
(g) Feel too hot.	Not during the past month	Less than once a week	Once or twice a week	Three or more times a week
(h) Had bad dreams.	Not during the past month	Less than once a week	Once or twice a week	Three or more times a week
(i) Have pain.	Not during the past month	Less than once a week	Once or twice a week	Three or more times a week

6. During the past month, how would you rate your sleep quality overall?

Very good

Fairly good

Fairly bad

Very bad

7. During the past month, how often have you taken medicine (prescribed or "over the counter") to help you sleep?

Not during the past month

less than once a week

Once or twice a week

Three or more times a week

8. During the past month, how often have you had trouble staying awake while driving, eating meals, or engaging in social activity?

Not during the past month

less than once a week

Once or twice a week

Three or more times a week

9. During the past month, how much of a problem has it been for you to keep up enough enthusiasm to get things done?

No problem at all

Only a very slight problem

Some what of a problem

A very big problem

Appendix III: Pittsburgh Sleep Quality Index

The FAST alcohol screening test

For the following questions please circle the answer which best applies.

1 drink = 1/2 pint of beer or 1 glass of wine or 1 single spirits

1 MEN: How often do you have EIGHT or more drinks on one occasion?
WOMEN: How often do you have SIX or more drinks on one occasion?

0	1	2	3	4
Never	Less than monthly	Monthly	Weekly	Daily or almost daily

2 How often during the last year have you been unable to remember what happened the night before because you had been drinking?

0	1	2	3	4
Never	Less than monthly	Monthly	Weekly	Daily or almost daily

3 How often during the last year have you failed to do what was normally expected of you because of drinking?

0	1	2	3	4
Never	Less than monthly	Monthly	Weekly	Daily or almost daily

[figure not shown]
4 In the last year has a relative or friend, or a doctor or other health worker been concerned about your drinking or suggested you cut down?

0	2	4
No	Yes, on one occasion	Yes, on more than one occasion

Appendix IV: FAST alcohol screening test

mHealth App Usability Questionnaire							
	Strongly agree						Strongly disagree
The app was easy to use	1	2	3	4	5	6	7
It was easy for me to learn to use the app	1	2	3	4	5	6	7
I like the interface of the app	1	2	3	4	5	6	7
The information in the app was well organised, so I could easily find the information I needed	1	2	3	4	5	6	7
I feel comfortable using this app in social settings	1	2	3	4	5	6	7
The amount of time involved in using this app has been fitting for me	1	2	3	4	5	6	7
I would use this app again	1	2	3	4	5	6	7
Overall, I am satisfied with this app	1	2	3	4	5	6	7
Whenever I made a mistake using the app, I could recover easily and quickly	1	2	3	4	5	6	7
This mHealth app provided an acceptable way to receive healthcare services	1	2	3	4	5	6	7
The app adequately acknowledged and provided information to let me know the progress of my actions	1	2	3	4	5	6	7
The navigation was consistent when moving between screens	1	2	3	4	5	6	7
The interface of the app allowed me to use all the functions (such as entering information, responding to reminder, viewing information) offered by the app	1	2	3	4	5	6	7
This app has all the functions and capabilities I expect it to have	1	2	3	4	5	6	7
The app would be useful for my health and well-being	1	2	3	4	5	6	7
The app improved my access to healthcare services	1	2	3	4	5	6	7
The app helped me manage my health effectively	1	2	3	4	5	6	7
The app made it convenient for me to communicate with my healthcare provider	1	2	3	4	5	6	7
Using the app, I had many more opportunities to interact with my health care provider	1	2	3	4	5	6	7
I felt confident that any information I sent to my provider using this app would be received	1	2	3	4	5	6	7
I felt comfortable communicating with my healthcare provider using the app	1	2	3	4	5	6	7

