1.2 RATIONALE FOR STUDY

Concussion is common and patients can go on to suffer with a constellation of symptoms which impacts their functional outcome and quality of life (McMahon *et al.*, 2013). Patient provision with information about their concussion and subsequent follow-up was highly variable in a prospective study in the USA (Seabury *et al.*, 2018). This is also the case with psychological therapies despite the fact there is evidence that CBT can help patients manage their symptoms after a concussion (Al Sayegh *et al.*, 2010).

We have developed HeadOn - a web application that delivers a CBT programme to patients following concussion. The application takes the patient through a 5-stage programme including: (i) understanding post-concussion symptoms; (ii) sleep after a concussion; (iii) lifestyle habits and exercise; (iv) managing negative thought patterns and (v) returning to baseline. The programme is delivered through a combination of weekly tasks (such as completing symptom diary, setting exercise goals and setting up a sleep time routine), audio/video media and reading material.

In this study, we would like to examine the feasibility of digitally delivering a course of CBT to patients following concussion. We hypothesise that patients will find it an acceptable and useful form of treatment. We plan on determining recruitment rates to guide future controlled trials.

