2 STUDY OBJECTIVES

2.1 OBJECTIVES

2.1.1 Primary Objective

Our primary objective is to determine the following regarding the digital delivery of CBT to patients following concussion:

- Compliance of participants with a digital CBT program
- Usability of a digital CBT program as a form of therapy

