2.2 ENDPOINTS

2.2.1 Primary Endpoint

1) Participant compliance with CBT program

Data inputted into the digital CBT program will be used as surrogate marker of participant compliance. During each stage of the program participants are required to input data as part of the CBT tasks. Participants will be divided into the following three groups: *Fully compliant*: participants who input data into the program during all five stages; *Partially compliant*: participants who input data but not during all five stages; *Non-compliant*: participants who do not enter any data into the program

2) mHealth App Usability Questionnaire

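### Four of the 21 usability items ask about communicating with a healthcare provider through the app, a function the plan does not describe; the form has no 'not applicable' answer and the plan no scoring rule.

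*Combined protocol and SAP*

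**What the plan says.** Section 2.1.1 gives as one of two primary objectives "Usability of a digital CBT program as a form of therapy", and Section 2.2.1 lists as the matching endpoint "2) mHealth App Usability Questionnaire", with nothing further. The form is printed in Appendix VI. It runs from "The app was easy to use" to a final item on comfort in communicating with a provider. Each item is rated from 1 (strongly agree) to 7 (strongly disagree), so a lower rating is better. No 'not applicable' column is printed.

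The last four items all refer to a provider. The first three read "The app made it convenient for me to communicate with my healthcare provider", "Using the app, I had many more opportunities to interact with my health care provider" and "I felt confident that any information I sent to my provider using this app would be received".

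Section 1.2 describes HeadOn as a staged self-help course: "The programme is delivered through a combination of weekly tasks", together with media and reading. Section 6 adds diaries, trackers, goal setting and automated reminders. Sections 8.2.1 to 8.2.6 cover demographics, recruitment, compliance, change in symptom scores, functional outcome and the symptom diary. The usability questionnaire appears in none of them.

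**The concern.** A questionnaire item is informative only if the respondent has met the thing it asks about. Here four items ask about a function that the plan does not attribute to HeadOn. A participant who never exchanged anything with a provider through the app could reasonably strongly disagree, choose the midpoint, or leave the item blank. The form does not steer them, and the staff who contact participants at week 5 have no instruction to give. Ratings could then differ between participants for reasons unrelated to how usable the app is.

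This affects one of the two primary endpoints. It is also hard to repair afterwards: once the form has been used as printed, a rating of 7 meaning 'this was bad' cannot be told apart from a 7 meaning 'this was not there'. Choosing between a 17-item and a 21-item summary after seeing the answers would also be open to challenge, particularly as Section 8.2 has the study PI perform the analysis.

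**Working it through.** **Is the function described?** These are the places where it would be expected to appear.

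- Section 1.2: five-stage course with tasks, media and reading. No provider contact is named.
- Section 6: daily symptom and mood diary, alcohol tracker, thought diary, goal setting, automated reminders. No provider contact is named.
- Appendix VII (home page): stage introduction, reminders, tasks, course progress, sharing icons, and an SOS icon whose function is not explained.
- Sections 3 and 6: staff contact at follow-up is by telephone, text or email from the research team. It is not described as happening inside the app.
- Table 2 in Section 7.1: the research nurses, classed there as part of routine care, have access to app data. This is access to data, with no exchange of messages described. It does mean that the item on information being received may partly apply.

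**How much of the form is affected?** Counting the items in Appendix VI gives 21, of which the last four name a provider. 4/21 = 19.0%.

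**What would a pooled mean do?** The plan states no score, threshold or expected value for this questionnaire, so there is no figure to reproduce. Suppose all 21 items were averaged. Let m be the mean of the other 17 items and x the mean of the four.

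- Pooled mean = (17m + 4x)/21
- Shift relative to the 17-item mean = (17m + 4x)/21 − m = 4(x − m)/21

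Both m and x are assumptions. Taking x = 4 (midpoint) and x = 7 (strongly disagree):

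| m | Pooled mean, x = 4 | Shift | Pooled mean, x = 7 | Shift |
|---|---|---|---|---|
| 2 | (34 + 16)/21 = 2.38 | +0.38 | (34 + 28)/21 = 2.95 | +0.95 |
| 3 | (51 + 16)/21 = 3.19 | +0.19 | (51 + 28)/21 = 3.76 | +0.76 |
| 4 | (68 + 16)/21 = 4.00 | 0 | (68 + 28)/21 = 4.57 | +0.57 |

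A positive shift is towards poor usability. The better the other 17 items are rated, the larger the shift for a given x.

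**When does the shift vanish or reverse?** It is zero when x = m, and also when the four items are left blank and the mean is taken over the items answered. It is negative when x < m: with m = 5 and x = 4, (85 + 16)/21 = 4.81, a shift of −0.19.

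**The case against.** A reader might infer that the usability score is biased towards 'poor'. The documents do not support that as a statement of fact. No pooled score is defined, so the shift arises only if the items are averaged together, and only if participants rate these four worse than the rest. Both are plausible, but neither is stated.

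A reader might also infer that HeadOn has no provider channel. That rests on silence. The SOS and menu icons are unexplained, nurses can see app data, and Section 9 provides for a high PHQ9 score, entered through the app, to be told to the participant, who is asked whether the GP may be informed. Information entered in HeadOn can therefore reach clinical staff, and the item on information being received is not plainly irrelevant. What stands is narrower: the plan describes no function for communicating with a provider through the app.

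The study is also a single-group, descriptive feasibility study with no usability cut-off, so no stated decision turns on half a point. Other items address satisfaction, reuse and usefulness directly, and the interviews cover ease of use and dislikes. It would go too far to say that the study cannot speak to acceptability. These points limit the consequence, but they do not tell staff or the analyst what to do with the four items.

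Finally, the line at 17 items involves judgement. Two retained items, on receiving and on accessing healthcare services, could be questioned for a self-directed programme. The line is drawn at items that name a provider, and prespecifying it makes the choice visible.

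**Conclusion.** The point holds as a mismatch between a primary-endpoint form and the intervention as described. Four of 21 items (19%) ask about communicating with a provider through the app, the plan describes no such function, the form gives no way to say so, and no scoring rule covers the result.

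The size is conditional. If all items are averaged and the four are rated 4 to 7, the mean worsens by 0.38 to 0.95 points when the others average 2, by 0.19 to 0.76 when they average 3, and by 0 to 0.57 when they average 4. These ratings are illustrative, since the documents supply none. A definite downward bias in the reported usability result should not be inferred. The firm conclusion is that answers to these items will be hard to interpret unless the form and the rule are settled before data collection.

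**What to change.** - Add a 'not applicable' response to the four provider items in Appendix VI.
- In Sections 2.2.1 and 8.2, prespecify that these four are reported item by item, with the count of 'not applicable' answers, and that the usability summary is the mean of the other 17 items (lower is better).
- Report the 21-item mean as a secondary figure, among participants who rated all 21 items, with the number contributing. Anyone who ticks 'not applicable' has no complete 21-item score, so this figure describes a subset and should be labelled as such.
- If HeadOn does have a provider channel, describe it in Section 1.2 and keep all 21 items in the score.

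The cost is a few sentences of analysis wording and a minor change to the form. The headline figure would no longer be the full 21-item score, which is why the secondary figure is kept.

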Appendix VI: mHealth App Usability Questionnaire (Zhou et al., 2019)

The screenshot shows the HeadOn app interface. At the top, there is a navigation bar with icons for a menu, home, chart, and SOS. The main header says "Hello [name]". Below this, a large box displays "You are on Stage 5 (Day 125)" with a "Getting back to baseline" icon. It also shows a "Stage Introduction" video player with a progress bar at 0:00 / 2:22. To the right, there are sections for "Today's Reminders" (empty), "Today's Tasks" (with buttons for "Set your goal", "Complete Symptom Diary", and "View Course Progress"), and social sharing icons for Twitter and Email. At the bottom, there are links for "Terms & Conditions" and "Privacy Policy" and the "headon" logo.

Appendix VII: HeadOn homepage showing reminder/task sections alongside the weekly audio which introduces the stage.

How do you feel today?				
Headache?				
None				Severe
Dizziness				
None				Severe
Sleep Disturbance				
None				Severe
Fatigue				
None				Severe
Feeling irritable				
None				Severe
Low mood				
None				Severe
Poor memory				
None				Severe
Difficulty concentrating				
None				Severe

Appendix VIII: HeadOn Symptom diary

What thoughts did you have about your concussion?

Type in what goes through your head about your concussion. For example, it was my fault I got a concussion because I'm clumsy.

Please tick all boxes that apply

What emotions did you feel?

Angry

NO Anxious

NO

Ashamed

NO Disgusted

NO

Guilty

NO Hopeless

NO

Happy

NO Overwhelmed

NO

Sad

NO Scared

NO

Worthless

NO

How distressed did you feel?

What thoughts did you have about your concussion?

Type in what goes through your head about your concussion. For example, it was my fault I got a concussion because I'm clumsy.

Evidence for

Type in evidence in favour of this thought. For example, I fall over a lot and got my concussion because of this

Evidence against

Type in evidence against this thought. For example, people trip up all the time and it isn't my fault that this happened

Appendix IX: HeadOn thought monitor

Interview Guide

Participants will be initially asked about their concussion and or/use of health apps. The list of topics asked to participants include;

1. About their experience of using the HeadOn
2. When and how they used the intervention
3. How easy or not easy they found the intervention to use
4. Likes and dislikes about the intervention
5. The functions which were most useful and least useful
6. What changes they would make to improve HeadOn

Appendix X: Qualitative interview schedule overview
